## Abstract

---

Chronic refractory cough in adults is defined as a cough lasting more than 8 weeks that does not resolve with treatment for asthma/eosinophilic airway disease, gastroesophageal reflux disease (GERD), or rhinosinusitis/post-nasal drip; and is not caused by smoking, ACE inhibitors, or parenchymal lung disease. It is one of the most common conditions leading to specialty referral, accounting for about 20% of new pulmonary consultations. Chronic refractory cough can lead to severe impairment of quality of life and social isolation as well as sleep deprivation and chronic fatigue. The few available treatments have limited benefit and substantial side effects or abuse potential. While there are validated tools to measure the health-impact of chronic cough which can provide feasible clinical trial outcome measures, there have been no academic multi-center trials of chronic cough, and guidelines for treatment continue to rely largely on opinion rather than evidence. The Pilot of Zinc Acetate to Improve Chronic Cough (ZICO) is a pilot study for a larger randomized clinical trial to establish the safety and tolerability of zinc acetate to treat cough in this population. The pilot trial will enroll 36 participants, 18 in each group, at 3 clinical centers. Participants will be 18 years or older, with chronic cough lasting at least 3 months, which has been unresponsive to treatments for asthma, GERD or other upper airway disease. Individuals that are current smokers, use an ACE inhibitor, currently take zinc supplements (or multivitamins with zinc), or whose medical history includes primary parenchymal lung disease, congestive heart failure, chronic kidney disease, pancreatitis, or another medical condition that could interfere with the study or are pregnant or breast-feeding will be excluded. Participants will be randomized to receive 6 weeks of treatment with either zinc acetate or placebo. Follow-up assessments will occur at 1, 3, 6 and 8 weeks after randomization; the final assessment, after a two week washout, will help establish the duration of treatment effect. The primary objective of the trial is to evaluate the feasibility of a full scale trial including estimating the statistical properties of the Cough Specific Quality of Life Questionnaire (CQLQ) and other measures of cough severity and overall health.

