## 2.6. Outcome measures

### 2.6.1. Patient Reported Outcomes

**Cough specific Quality of Life (CQLQ):** This is a 28 item self-completed questionnaire with six subscales with excellent psychometric properties (Cronbach alpha = 0.92, ICC = 0.89) that is responsive to treatment. The estimates of the standard deviation are consistent (12-15) across studies. A minimum clinically important difference of 5 has been proposed, which is based upon a small single center study of idiopathic pulmonary fibrosis and has not been validated in a larger, multicenter cohort.

**Leicester cough questionnaire (LCQ):** The LCQ is a patient reported cough outcome measure which has been validated and will be used to assess convergent validity for the CQLQ. The LCQ has similar properties as the CQLQ with 19 items and 3 domains, with a total possible score ranging from 3 to 21. The minimal important difference of the LCQ for patients with chronic cough is 1.3.

**Cough visual analog scales, overall, daytime, nighttime, urge to cough (C-VAS):** The C-VAS is a patient reported cough outcome measure that provides a measure of the severity, intensity and noxious qualities of cough that are not as well represented on the health impact scales. Each element of the VAS has a possible score of 0 to 100.

**EuroQol EQ-5D- 5L:** The EQ-5D-5L is an overall measure of health related quality of life that provides a measure of utility for calculation of Quality Adjusted Life Years (QALYs). The EQ-5D measures 5 dimensions: mobility, self-care, usual activities, pain/discomfort, and anxiety/depression graded from level 1 (i.e., no problems) to level 5 (i.e., extreme problems). Use of the 5-levels (EQ-5D-5L) rather than the standard 3 level EQ-5D (EQ-5D-3L) decreases the ceiling effect, improves discriminative ability, and potentially has more power to detect differences between groups.

**Cough-related Impact on Quality of Life Scale (Cough IQOLS):** This is a health related quality of life measure that includes the impact of cough adapted from Sandra Wilson's Asthma Impact on Quality of Life Survey (AQOLIS).

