### 3.2. Randomization

Participants will be randomized to zinc acetate or placebo at V2. Treatment assignment will be randomly allocated in a 1:1 ratio with stratification by clinic with permuted block design will be used. Assignments will be released from the DCC after evidence that an eligible participant has signed consent and completed all baseline evaluations.

Zinc acetate or placebo will be dispensed to the participant at the V2 visit. At randomization the participant will be assigned a unique bottle ID code and clinics will dispense that bottle to the participant. Each participant will receive a single bottle of 168 capsules for the 6 weeks of treatment. At the second to last study (V5) visit, the bottle with the unused capsules will be returned.

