### **4.1. Sample size**

The primary goals of the pilot study are to establish the feasibility of performing a randomized trial and to obtain preliminary estimates of the relative efficacy of zinc versus placebo and the statistical properties of the patient reported outcome measures. A sample size of 36 (18/arm) has 80% power to detect a treatment effect of 0.56 standard deviations (SD) or greater, where SD is for the difference from baseline to 6 weeks in CQLQ score, based upon a two-sample t-test and a one-sided type 1 error rate of 0.20. We are conducting a contemporaneous cohort study to establish the minimal important difference (MID) and SD for change in CQLQ scores in 100 participants with chronic cough. This analysis will not necessarily provide information whether the changes are clinically important, but will provide a framework for establishing changes that are outside of the range of variability of symptoms and would be noticeable by the patient. Thus, in

this context, the MID would be analogous to the “Just Noticeable Difference” (JND) used in psychophysics of perception.

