### Primary Analysis

The primary analysis will focus on the tolerability of zinc acetate versus placebo. These analysis will rely on qualitative assessments of adverse drug effects as well as unadjusted comparisons of the frequency of events and adherence by treatment assignment.

The statistical analysis for efficacy will be an unadjusted comparison of 6-week change in CQLQ between treatment groups. A linear mixed effects model will be used to model change in CQLQ over time. A saturated means model with indicators for each time point, treatment and treatment by time interaction, will be specified and a random effect for individual will be used to account for the repeated measurements over time. The 6-week treatment by time interaction term represents the difference in change in CQLQ between the treatment groups, i.e. the primary outcome. If the data are non-normal, then transformations and non-parametric alternatives (e.g. Wilcoxon Rank-Sum test comparing the raw differences from baseline to 6-weeks between treatment groups) will be explored. Using the methods described by Cocks and Torgerson, we will test whether or not the upper boundary of the 1-sided 80% confidence interval of the treatment effect excludes the MID. For example, a total sample size of 36 would be sufficient to exclude a MID of 5 or higher for a 1-sided 80% confidence interval if the standard deviation for the change in CQLQ was 15. Sensitivity analyses using alternate mean and covariance structures will also be performed. Analyses will be done based upon principles of intention to treat, i.e. all data from all randomized participants will be included in the analysis.

Secondary outcomes include, but are not limited to, LCQ, diary data, C-VAS, GACC, quality of life measures, and safety data. Continuous variables will be analyzed similarly to the primary outcome. Event outcomes will be analyzed in two ways: negative binomial regression for rates and Kaplan-Meier curves and Cox proportional hazards models for time to first event.

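### Randomization is stratified by clinic but the CQLQ model has no clinic term; if clinics differ in mean change, the one-sided 80% limit is somewhat too wide

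*Combined protocol and SAP*

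**What the plan says.** Section 3.2 (Randomization): "Treatment assignment will be randomly allocated in a 1:1 ratio with stratification by clinic with permuted block design will be used". The Abstract gives 36 participants, "18 in each group, at 3 clinical centers".

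The Primary Analysis text in section 4 states: "The statistical analysis for efficacy will be an unadjusted comparison of 6-week change in CQLQ between treatment groups". The mixed model has indicators for visit, treatment and treatment by visit, plus a random effect for the participant. The effect of interest is the 6-week treatment-by-time term. Clinic is not among the terms. Sensitivity analyses with other mean and covariance structures are promised, but clinic is not named there either, and no reason is given for leaving it out.

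The upper one-sided 80% limit for this effect is compared with the MID. The futility paragraph of section 4 says a definitive trial is unlikely if the limit excludes the MID, and also that no single measure will decide. Continuous secondary outcomes are to be analysed in the same way as the CQLQ.

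**The concern.** Blocks within clinic keep the two arms nearly balanced in each clinic. A difference between clinics in mean CQLQ change therefore affects both arms alike and largely drops out of the treatment contrast. A model without clinic does not know this and leaves the difference in the residual variance. Its standard error then exceeds, on average, the true sampling error of the contrast.

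What is at stake is the 80% limit. With the plan's own example (MID 5, SD 15, 36 participants) the half-width is a little over 4 points, so less than one point separates it from the MID when the observed effect is zero. A limit that is too wide makes the MID harder to exclude and so favours going on to a definitive trial.

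**Working it through.** **Inputs.** 18 per arm, from section 4.1: "A sample size of 36 (18/arm) has 80% power to detect a treatment effect of 0.56 standard deviations (SD) or greater", "based upon a two-sample t-test and a one-sided type 1 error rate of 0.20". SD of change 15, from the Primary Analysis example: "if the standard deviation for the change in CQLQ was 15". Section 2.6.1 gives 12 to 15 for the CQLQ. MID 5 and the one-sided 80% limit come from the same example. Three clinics come from the Abstract. Assumed, because the documents do not give them: 12 participants per clinic, exact balance by arm within clinic, complete data, and the share *s* of the variance of change that lies between clinics.

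**The plan's own figures.** Power: 0.56 × √(18/2) = 1.68; 1.68 − 0.842 = 0.838; Φ(0.838) = 79.9% (79.7% with the noncentral t). Half-width at SD 15: 0.842 × 15 × √(2/18) = 4.21, or 4.26 with t on 34 df. Both are below 5. The stated 80% and the MID example reproduce.

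**Which clinic differences matter.** In one simulated data set, clinic level shifts of −10/0/+10 left the standard error of the 6-week interaction at 4.579, the same as with no shift. Adding a clinic main effect also left it at 4.579. Shifts in change of −5/0/+5 raised it to 4.648. With clinic-by-visit included it was 4.663 in every case. So only differences in change enter the error, only clinic-by-visit removes them, and the gain is an average one that need not appear in each data set.

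**Size in the planned model.** CQLQ is taken at four visits (weeks 0, 3, 6, 8). Let *b* = 225*s* be the between-clinic part of the variance of change and *w* = 225(1 − *s*) the rest. The residual variance per visit is *w*/2. Take the clinic offsets as fixed and equal at all three post-baseline visits.

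- A shift *d* after baseline only has a within-person sum of squares of (9/16 + 3/16)*d*² = 0.75*d*². Over 36 participants this adds 36 × 0.75 × *b* = 27*b*.
- Residual df without clinic: 34 × 3 = 102. Expected mean square: *w*/2 + 27*b*/102.
- Standard error without clinic: √(mean square × 2 × 2/18). With clinic and clinic-by-visit: √(*w*/2 × 2 × 2/18), on 96 df.
- One-sided 80% multiplier: 0.845 in both cases.

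Worked at *s* = 20%: *b* = 45, *w* = 180. Without clinic: 90 + 27 × 45/102 = 101.9; SE = √(101.9 × 4/18) = 4.76; half-width 4.02. With clinic: SE = √(90 × 4/18) = 4.47; half-width 3.78. Averages over 20,000 simulated trials per setting are about 0.01 lower, because a standard error averages slightly below the root of its mean square:

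| Assumed clinic share of variance of change | Half-width, no clinic | Half-width, clinic and clinic-by-visit |
|---|---|---|
| 0% | no difference | no difference |
| 5% | 4.17 | 4.11 |
| 10% | 4.11 | 4.00 |
| 20% | 4.01 | 3.77 |

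**Coverage.** At 20% the true SE is 4.47, so Φ(4.02/4.47) ≈ 82% without clinic, against the nominal 80%. At 5% the simulated coverage stays within about half a point of 80%.

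**Chance of excluding a MID of 5 when there is no effect.** 57% to 58% at a 10% share; 58% to 61% at 20%.

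**What the shares mean.** With offsets −*d*/0/+*d*, *b* = (2/3)*d*². A 10% share (*b* = 22.5) is *d* = 5.8 points, and 20% (*b* = 45) is *d* = 8.2. Both exceed the example MID of 5, so they are large clinic differences.

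**The case against.** The best defence is that the effect is conditional and probably small. Nothing in the documents shows that clinics differ in mean change, and at 0% there is no loss. The participant random effect absorbs level differences. Residual variance is pooled over four visits, which dilutes the excess at week 6. If clinic effects are drawn at random rather than fixed, the added sum of squares falls from 27*b* to 18*b* and the gain shrinks further. This is also a pilot with feasibility aims, and the promised sensitivity analyses could accommodate clinic. All of that stands. It limits the size; it does not explain why the one design factor is left out of the primary model.

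A reader might infer more than the documents support:

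- *That all clinic differences inflate the error.* They do not; only differences in change do.
- *That the 80% limit is invalid, or the estimate biased.* The limit over-covers if anything, and with balanced arms the estimate is the same with or without clinic.
- *That the limit alone decides futility.* Section 4 says no single measure will.
- *That the tolerability analysis shares the fault.* The plan does specify "unadjusted comparisons of the frequency of events and adherence by treatment assignment", but these comparisons do not feed the 80% limit, and the documents say nothing about clinics differing in how they elicit events or adherence. Clinic-stratified estimates there are optional and may be unstable with sparse events.

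**Conclusion.** The mismatch is certain: clinic is a stratification factor, and the CQLQ analysis is unadjusted with no clinic term. The consequence is conditional. If clinics differ in mean change, the 80% limit is too wide by about 0.06 points at a 5% clinic share, 0.11 at 10% and 0.24 at 20%, with coverage near 82% at 20%. The direction favours proceeding. These figures assume SD 15, three equal clinics, complete data, and fixed offsets equal at all post-baseline visits. The clinic share is not in the documents and is the assumption that matters most. The change is worth making because it costs almost nothing, not because the expected harm is large.

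**What to change.** State that the CQLQ mixed model includes clinic and clinic-by-visit as fixed effects, and that the continuous secondary outcomes are analysed likewise. Clinic as a covariate in an analysis of 6-week change serves the same purpose. A clinic main effect alone does not. Keep the unadjusted result as a sensitivity analysis, and settle the wording before unmasking. If the sponsor prefers to omit clinic, the plan should give the reason.

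Cost: a sentence of text and 8 extra mean parameters (2 for clinic, 2 × 3 for clinic by visit), which doubles the 8 already in the model (4 visits × 2 arms). At the week-6 contrast this amounts to about 2 error degrees of freedom. If clinics do not differ, the half-width in an analysis of change goes from 4.262 (t on 34 df) to 4.265 (t on 32 df).

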**Inclusion criteria:**

- Men or women age 18 or older
- Chronic cough for more than 3 months
- No upper or lower respiratory infection within 4 weeks
- Either
  - Negative evaluation for:
    - Asthma; no symptoms of disease or no evidence of asthma based on spirometry and/or methacholine challenge test
    - GERD: no symptoms of acid reflux disease or negative pH probe
    - Rhinosinusitis/upper airway cough

Or

- Cough persists despite treatment for the following potential causes:
  - Asthma –treated for at least 8 weeks with at least medium dose inhaled corticosteroids or with oral corticosteroids
  - GERD – treated for at least 8 weeks with either a proton pump inhibitor (PPI) or H2 blocker
  - Upper airway disease, postnasal drip or sinusitis – treated for at least 8 weeks with nasal steroids, antihistamines or both.
- Non-smoker; defined as
  - no smoking of any substance (e.g., tobacco, e-cigarette, marijuana) in the past 6 months, and
  - less than 20 pack-year smoking history
- Chest x-ray or CT scan in the past 24 months and after the onset of cough; negative for parenchymal lung diseases (such as interstitial lung disease, idiopathic pulmonary fibrosis, pneumonia, or TB) and negative for lung cancer
- Overall Cough VAS score of 30 or higher at V1
- Willing to halt use of zinc supplements or multivitamins containing zinc for the duration of the study
- Provide written consent

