## 2.4. Summary of visits

### Visit 1 Screening Visit (week -1, 2 hours)

- Consent
- Eligibility assessment
  - Chest x-ray, if participant does not have chest x-ray or CT from within the past 2 years
- Cough Visual Analog Scales (C-VAS)
- Baseline medical history
- Spirometry (pre- and post-bronchodilator)
- Pregnancy test for women of child-bearing potential
- Blood draw for creatinine level, serum zinc and copper levels, and biospecimens
- Explain and distribute cough diary

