### Visit 2 Baseline / Randomization (week 0, 2 hours)

- Interval medical history
- Collect and review cough diary
- Cough questionnaire completion
  - Cough Visual Analog Scales (C-VAS)
  - Cough Quality of Life Questionnaire (CQLQ)
  - Leicester Cough Questionnaire (LCQ)
  - Global Assessment of Change in Cough (GACC)
  - Cough-related Impact on Quality of Life Scale (Cough IQOLS)
  - EQ-5D
- Physical examination
- Eligibility review and randomization
- Dispense study treatment

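### C-VAS is scored twice before treatment, but the analysis carried over from CQLQ uses only one of the two scores; adjusting for both would tighten this secondary comparison

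*Combined protocol and SAP*

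**What the plan says.** The data collection schedule (section 2.5) and the visit lists (section 2.4) place C-VAS at V1, V2, V4, V5 and V6. V1 is the screening visit at week -1. V2 is at week 0, carries the label Baseline / Randomization, and is when study drug is dispensed. CQLQ, LCQ, GACC, Cough IQOLS and EQ-5D start only at V2, so C-VAS is the one questionnaire scheduled at both visits.

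The only stated use of the V1 score is for entry: "Overall Cough VAS score of 30 or higher at V1" (section 2.2, inclusion criteria).

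Under Primary Analysis, C-VAS is a named secondary outcome, and the method is: "Continuous variables will be analyzed similarly to the primary outcome". The method carried over is an unadjusted comparison of 6-week change, from a mixed model with a saturated mean (time, treatment and their interaction) and a random effect per individual. The 6-week interaction is the effect. Nothing says how a second pre-treatment score should enter.

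**The concern.** The rule was written for CQLQ, which has a single pre-treatment score, so the question of a second one does not arise there. For C-VAS it does. A saturated mean gives each visit its own parameter in each arm. The week-6 interaction is then the difference between arms in change from one reference visit, and a second pre-treatment visit uses up its own parameters without informing that difference.

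With 18 per arm, precision is the main limit. Section 4 bases the decision on a definitive trial partly on the size and consistency of the treatment effect across the evidence. It does not name C-VAS there, but a secondary cough outcome can reasonably be expected to inform that judgement. A wider interval than necessary makes consistency harder to judge, and the unused score has already been collected.

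**Working it through.** **Inputs from the documents.** 18 per arm; 1:1 allocation; C-VAS at V1, V2 and week 6; random-intercept model, unadjusted. **Assumed**, because the documents do not give them: the correlations of C-VAS between visits.

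**1. The plan's own power figure.** Section 4.1: "A sample size of 36 (18/arm) has 80% power to detect a treatment effect of 0.56 standard deviations (SD) or greater", "based upon a two-sample t-test and a one-sided type 1 error rate of 0.20". The SD is that of the 6-week change in CQLQ. Normal approximation: 0.56 × √(18/2) = 1.68; 1.68 − 0.842 = 0.838; Φ(0.838) = 79.9%. The noncentral t with 34 df gives 79.7%. The figure reproduces. There is no corresponding figure for C-VAS.

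**2. Does V1 help if it enters as another time point?** The stated model was fitted to one complete simulated data set of 36 (between-person SD 16, residual SD 12).
- Without V1: week-6 interaction −2.920, SE 6.24.
- With V1 as an extra time point: −2.920, SE 6.08.
- Raw difference between arms in change from V2 to week 6: −2.920.

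The estimate is identical. The SE moves only because the residual variance is re-estimated. V1 contributes nothing to the contrast itself.

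**3. Precision by method.** Set the variance at each visit to 1. Let a = corr(V1, V2), b = corr(V2, week 6), c = corr(V1, week 6).
- Unadjusted change from V2: 2(1 − b).
- V2 as covariate: 1 − b².
- V1 and V2 as covariates: 1 − (b² + c² − 2abc)/(1 − a²).
- Change from the V1/V2 mean: 1 + (1 + a)/2 − b − c.

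Example with all correlations 0.5: the first three variances are 1.00, 0.75 and 0.667. The SE ratio for both covariates against change from V2 is √0.667 = 0.816.

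SE ratios:

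| a, b, c (assumed) | Both covariates vs change from V2 | V2 covariate vs change from V2 | Both vs V2 covariate | Change from mean vs change from V2 |
|---|---|---|---|---|
| 0.4, 0.4, 0.4 | 0.802 | 0.837 | 0.958 | 0.866 |
| 0.6, 0.6, 0.6 | 0.829 | 0.894 | 0.927 | 0.866 |
| 0.7, 0.7, 0.7 | 0.840 | 0.922 | 0.911 | 0.866 |
| 0.8, 0.8, 0.8 | 0.850 | 0.949 | 0.896 | 0.866 |
| 0.8, 0.7, 0.65 | 0.901 | 0.922 | 0.978 | 0.957 |
| 0.8, 0.6, 0.5 | 0.894 | 0.894 | 0.999 | 1.000 |
| 0.9, 0.7, 0.6 | 0.918 | 0.922 | 0.995 | 1.041 |

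The first four rows have equal correlation, as the plan's random-intercept model implies. In the last three, correlation decays with time. Milder decay falls in between: 0.7, 0.6, 0.55 gives 0.871 in the first column.

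**4. Selection on V1 ≥ 30.** Simulation with an assumed mean of 50-55, SD 20-25 and equal correlation 0.4-0.8, scores held to 0-100, gave 0.801-0.850 for both covariates against change from V2, and 0.908-0.974 for both against V2 alone. The entry threshold does not remove the gain.

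**5. Small-sample cost.** The ratios in step 3 ignore the cost of estimating the covariate slopes. For p normally distributed covariates, chance imbalance multiplies the expected variance by (N − 3)/(N − 3 − p). With N = 36 and p = 2 this is 33/31 = 1.065, or 1.032 on the SE. With p = 1 it is 33/32, or 1.016 on the SE. Multiplying by 1.032 turns 0.802-0.850 into about 0.83-0.88, and 0.894-0.918 into about 0.92-0.95. Simulated trials of 36 agreed: 0.83-0.88 and 0.92-0.94.

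**The case against.** The strongest reply is that this is a preference for efficiency and not an error. The plan chooses an unadjusted comparison, and that comparison is valid. All data from all randomized participants are to be included, and sensitivity analyses with other mean and covariance structures are planned. What stands is that nothing is biased. But including V1 as a time point does not use its information (step 2), and the sensitivity sentence does not commit to using V1.

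A second reply is that V1 itself adds little. This largely stands. In the decay settings nearly all the gain comes from having V2 as a covariate, and V1 adds 0-2%, which its own small-sample cost of about 1.6% can cancel. At equal correlations of 0.4-0.6, V2 also gives the larger part. Only at 0.7-0.8 does V1 give more (9-10%).

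Three stronger readings are tempting, and the documents do not support them:
- A reader might infer that averaging V1 and V2 is worth 13% of the SE, or 24 instead of 18 per arm (18/0.75). That requires equal correlation between all visits. V1 and V2 are one week apart, while week 6 is six and seven weeks away. With decay, change from a fixed mean can gain nothing or lose precision (last column of the table).
- A reader might infer that change will be measured from V1, a score selected to be high, so that regression to the mean would pass for improvement. The plan does not state such an analysis: V2 is the visit labelled Baseline.
- A reader might infer that the trial's power or its go/no-go rule is weakened. Both rest on CQLQ, which has one pre-treatment score.

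**Conclusion.** The point holds as a minor one. The C-VAS analysis carried over from CQLQ leaves a pre-treatment score unused and is less precise than an adjusted analysis, with no bias in the comparison between arms. That V2 is the intended reference is inferred from its label; the conclusion is the same for any single reference visit.

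Against unadjusted change from V2, adjustment for both scores lowers the large-sample SE by about 15-20% under equal correlation (0.4-0.8) and by about 8-11% in the three decay settings. After the cost of estimating two slopes in 36 participants, that is roughly 12-17% and 5-8%. V1's own share beyond V2 is about 0-10% before its cost. All of these figures rest on assumed correlations and equal variances across visits. The consequence is confined to a secondary outcome.

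**What to change.** Add one sentence for C-VAS under secondary outcomes, before unmasking: the week-6 comparison between arms adjusts for the V1 and V2 scores of the same scale as two separate covariates, not as change from a fixed V1/V2 mean, and within-arm change is reported from V2. The model then takes the post-randomization visits as outcomes and keeps the treatment-by-visit terms.

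The cost is one degree of freedom more than adjusting for V2 alone. No new data, visit or procedure is needed. The CQLQ analysis, the sample size and the futility rule stay as they are.
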